8.4.1 Adverse Events

Treatment-emergent AEs will be defined as those occurring coincident with start of treatment through 46 days post-treatment (Day 60).

In the favipiravir + SOC arm: Adverse event solicitation and recording will begin immediately following the first dose of favipiravir and will include only on-treatment (treatment emergent) events. Any changes to a subject's health that occur between the signing of the informed consent and dosing will be recorded as updates to the subject's medical history.

In the SOC alone arm: Adverse event solicitation and recording will begin following the completion of all baseline assessments.

Subjects will be instructed to report AEs during the study and staff will query subjects regarding AEs throughout the study. The Investigator (and/or designee) must document all AEs reported through completion of the Day 60 visit. Any subject who is withdrawn from the study due to an AE shall be followed until the event has resolved or stabilized or, if in the favipiravir arm, 14 days after last dose. The Investigator will document available follow-up information on the subject's source documentation and CRF.

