7.1 Day 1 (PRE-DOSE)

- Obtain informed consent.
- Verify eligibility per the inclusion and exclusion criteria. (See Sections 5.1 and 5.2)
 - o Review and record medical history, including tobacco use, to ensure there are no exclusionary illnesses.
 - Review and record concomitant medications for possible prohibited medications. (See Section 6.7)
- If subject is female of child-bearing potential and meets inclusion criteria 4.c, obtain urine or blood pregnancy test and proceed it result is negative.
- Measure and record vital signs (BP, HR, Temp, Resp).
 - **NOTE:** vital signs to be recorded and entered in the EDC every day while subject is in the hospital and on return study visits after discharge.
- Perform Physical exam (may be done by the Principal Investigator or their designee)
- Assess and record baseline clinical status according to the following study-specific 6-point scale:
 - 1. Not hospitalized
 - 2. Hospitalized, not requiring supplemental oxygen
 - 3. Hospitalized, requiring supplemental oxygen
 - 4. Hospitalized, on non-invasive ventilation or high flow oxygen devices
 - 5. Hospitalized, on invasive mechanical ventilation or ECMO

6. Death

NOTE: Clinical Status to be recorded and entered in the EDC every day while subject is in the hospital and on return study visits after discharge.

- Assess and record NEWS2 (See charts by clicking this link: https://www.rcplondon.ac.uk/projects/outputs/national-early-warning-score-news-2
 - **NOTE:** NEWS2 assessment to be recorded and entered in the EDC every day while subject is in the hospital and on return study visits after discharge.
- Assess and record ECOG Performance Status and Study-specific Symptom Status (see Appendix A).
 - **NOTE:** ECOG Performance Status and Study-specific Symptom Status to be collected and recorded every day while the subject is in the hospital and on return study visits after discharge.
- Collect nasopharyngeal and oropharyngeal swabs for virologic testing. (See Virology Laboratory Manual.)
- Collect blood samples for:
 - o Antibodies to SARS-CoV-2.
 - o Hematology and clinical chemistry laboratory analyses
- Collect and record SpO2 by Finger Sensor
 - **NOTE:** SpO2 to be recorded and entered in the EDC every day while subject is in the hospital and on return study visits after discharge.
- Perform subject randomization (via EDC) to establish treatment arm (favipiravir + SOC or SOC alone).

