8.4.3 Evaluating and Reporting of Adverse Events

All AEs (i.e. a new event or an exacerbation of a pre-existing condition) that occur after dosing with favipiravir and after completion of baseline assessments in the SOC alone arm, must be recorded as an AE or SAE (if applicable), on the Adverse Event eCRF and SAE form, as applicable. The Investigator must follow all AEs until the AE resolves, or until the Investigator and/or the Medical Monitor determine the event is chronic or clinically stable. If an AE remains unresolved at the conclusion of the study, the Investigator and Medical Monitor will make a clinical assessment to determine whether continued follow-up of the AE is warranted. All subjects who have received at least one exposure to study therapy will be evaluated for safety of study treatment.

The Investigator should attempt to establish a diagnosis of the event based on signs, symptoms and/or other clinical information. In such cases, the diagnosis should be documented as the AE and not the individual signs/symptoms.

All AEs must be promptly documented on the Adverse Event eCRF and assessed by the Investigator. Details of the event must include the dates of onset and resolution, severity, relationship to study drug, seriousness, and whether the event caused the subject to withdraw from the study, outcome and timing with regard to administration of the study drug.

Severity: Severity should be graded and recorded as follows:

- Mild: Awareness of event but easily tolerated
- Moderate: Discomfort enough to cause interference with usual activity
- Severe: Inability to carry out usual activity, incapacitating, requires medical intervention

Relationship: The relationship of the Adverse Event to the study drug will be determined by the Principal Investigator, and assessed using the following definitions:

• **Related:** There is a distinct temporal relationship between the event onset and administration of the study drug. There is a known reaction to agent or chemical group or

predicted by known pharmacology. The event cannot be explained by subject's clinical state or other factors.

• Unrelated: Evidence exists that the AE has an etiology other than the study drug (e.g., pre-existing condition, underlying disease, intercurrent illness, or concomitant medication).

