8.4.4 Serious Adverse Events (SAEs)

All SAEs as defined below and that occur after the first dose of favipiravir and up to Day 60 (which is 46 days after the last planned study drug administration) must be reported to the Sponsor as soon as the site becomes aware of them. Any SAEs occurring after Day 60 (more than 46 days after last planned study drug administration) and considered at least possibly drug-related must also be reported.

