#### 4.5.2. Adverse Events

All AEs will be coded using the MedDRA v23.0 coding system and displayed in tables and data listings using system organ class and preferred term. Missing and partial dates will be handled as described in [Section 3.10.2](#).

Treatment-emergent AEs (TEAEs) will be defined as those occurring coincident with start of treatment through Day 60.

In the favipiravir + SOC arm: Adverse event solicitation and recording will begin immediately following the first dose of favipiravir and will include only on-treatment (treatment-emergent) events. Any changes to a subject's health that occur between the signing of the informed consent and dosing will be recorded as updates to the subject's medical history.

In the SOC alone arm: Adverse event solicitation and recording will begin following the completion of all baseline assessments.

Clinical events related to the progression of COVID-19 will **not** be considered AEs.

Adverse events are summarized by subject incidence rates; therefore, in any tabulation, a subject contributes only once to the count for a given AE in both SOC and preferred term.

The number and percentage of patients with any TEAE, with any TEAE assessed by the Investigator as related to treatment, with any serious TEAE, and with any treatment-emergent serious AE (SAE) potentially related to treatment will be summarized by treatment group and overall.

All AEs occurring on-study will be listed in subject data listings.

By-subject listings also will be provided for the following: subject deaths, SAEs, and AEs leading to treatment/study discontinuation.

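### Adverse event recording starts at a different point in each arm, and start of treatment is undefined for SOC TEAEs

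*Protocol*

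**What the plan says.** Protocol 8.4.1 gives one recording rule per arm. For favipiravir plus SOC: "Adverse event solicitation and recording will begin immediately following the first dose of favipiravir". For SOC alone: "Adverse event solicitation and recording will begin following the completion of all baseline assessments". Protocol 8.4.3 turns the same split into an eCRF rule, covering events "that occur after dosing with favipiravir and after completion of baseline assessments in the SOC alone arm, must be recorded as an AE". SAP 4.5.2 repeats both rules, including the treatment of the pre-dose period in the favipiravir arm: "Any changes to a subject's health that occur between the signing of the informed consent and dosing will be recorded as updates" to the medical history.

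Both documents define TEAEs as events from start of treatment through Day 60 (Protocol 8.4.1 and 9.7, SAP 4.5.2). None of these sections says when treatment starts for a SOC subject. SAP 3.5 does supply a SOC origin, the randomization date, but only for time-to-event analyses.

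Two further rules depend on a dose that SOC subjects never receive. Protocol 8.4.4 sets the SAE reporting window as "All SAEs as defined below and that occur after the first dose of favipiravir and up to Day 60". SAP 3.10.2 imputes partial AE onset dates by reference to the first dose.

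**The concern.** Comparing the safety of favipiravir plus SOC with SOC alone is a stated secondary objective (Protocol 4.2), and Protocol 9.7 plans differences in TEAE proportions between the arms. That comparison needs the same period at risk in both columns.

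Here the period is set by arm. Between randomization and first dose, the same event goes to medical history in one arm and to the AE form in the other. The difference arises at collection: favipiravir events in that period never reach the AE dataset, so programming alone cannot restore them. Any resulting distortion raises the SOC count and makes favipiravir look slightly better.

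**Working it through.** **Step 1: where an event goes, by time of onset.** The order follows Protocol 7.1 and 7.2, which list the baseline assessments, then "Perform subject randomization (via EDC) to establish treatment arm", then the pre-dose PK sample, then the first dose.

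| Onset | Favipiravir + SOC | SOC alone |
|---|---|---|
| Consent to end of baseline assessments | Medical history | Before recording starts |
| End of baseline assessments to randomization | Medical history | Not settled: the wording of 8.4.1 would allow recording, but the arm is not yet known |
| Randomization to first dose | Medical history | Recordable as an AE, if baseline assessments are complete |
| After first dose (or the same time in SOC) to Day 60 | AE | AE |

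The third row is the defect, and it remains on the narrowest reading of the text.

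**Step 2: does the TEAE definition remove it?** If start of treatment for SOC means randomization, as in SAP 3.5, the third row still counts as a TEAE in SOC. If it means completion of baseline assessments, the third row also counts. If it means the Day 1 post-dose column, where both schedules first mark AE solicitation, a SOC subject has no dose to locate it. No stated definition closes the gap.

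**Step 3: size.** The documents give no figure to reproduce. The inputs are:

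- Subjects per arm: about 25 (Protocol 9.2).
- Gap g from randomization to first dose: assumed 1 to 24 hours. Protocol 7.2 says only that dosing should follow eligibility as quickly as possible.
- Proportion p of SOC subjects with a TEAE in the rest of the window: assumed 0.3 to 0.8.
- Period T over which that risk is spread: assumed 60 days (constant risk) or 14 days (risk concentrated early).

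A gap event changes the any-TEAE count only if the subject has no later TEAE. With constant hazard λ = −ln(1 − p)/T, the extra share is (1 − p) × (1 − exp(−λg)).

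For g = 24 hours (1 day) and p = 0.63:

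- T = 60: λ = 0.994/60 = 0.0166. Extra = 0.37 × 0.0164 = 0.0061, or 0.15 of 25 subjects.
- T = 14: λ = 0.994/14 = 0.0710. Extra = 0.37 × 0.0686 = 0.0254, or 0.63 of 25 subjects.

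Other values with T = 14:

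| g | p | Extra (percentage points) | Of 25 |
|---|---|---|---|
| 24 h | 0.3 | 1.76 | 0.44 |
| 24 h | 0.5 | 2.42 | 0.60 |
| 24 h | 0.8 | 2.17 | 0.54 |
| 6 h | 0.63 | 0.65 | 0.16 |
| 1 h | 0.63 | 0.11 | 0.03 |

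The 0.63 is the ceiling over all p for this gap and T. The expression peaks where 1 − p = (14/15)^14 = 0.381, and its value there is 0.381/15 = 0.0254.

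**The case against.** The strongest reply is that the gap is meant to be short, that clinical events of COVID-19 progression are not AEs (Protocol 8.4.2, SAP 4.5.2), and that the safety summaries are descriptive, with no test, in an exploratory study of about 50 subjects. All of this stands, and it keeps the effect small. It does not make the two windows equal.

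Several stronger readings are tempting, and the documents do not support them.

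- *SOC recording opens before randomization.* A reader might infer this from the list order in Protocol 7.1, but no rule states it. An arm-specific start cannot be applied prospectively before the arm is known, both schedules place the first AE solicitation under Day 1 post-dose, and SAP 3.5 lets the SOC baseline measurement fall after randomization.
- *Several SOC subjects are added.* With an assumed 0.3 events per day and a 24-hour gap, 25 × (1 − exp(−0.3)) = 6.5 SOC subjects would have an event in the gap. That is not the change in the any-TEAE count. If the same rate held for 14 days, only exp(−4.2) = 0.015 of subjects would have no later event, so the net addition is 6.5 × 0.015 = 0.10. At 0.1 per day it is 25 × 0.0952 × exp(−1.4) = 0.59.
- *The favipiravir window also closes early.* The clause "or, if in the favipiravir arm, 14 days after last dose" concerns follow-up of a subject withdrawn from the study for an AE, and that event is already counted. Protocol 8.4.1 requires AEs to be documented through the Day 60 visit, and 5.4 keeps subjects who stop treatment in the study.
- *The SAE window adds to the tilt.* Read literally, the anchor in Protocol 8.4.4 would leave out SOC SAEs, which runs the other way. Protocol 8.4.3 has SOC SAEs recorded in any case.

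**Conclusion.** The point holds in a limited form. The AE start differs by arm in explicit text, and start of treatment is undefined for SOC TEAEs. An event between randomization and first dose can count in SOC and not in favipiravir.

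For events in that period the tilt is towards favipiravir, provided SOC baseline assessments are complete by randomization; if they finish later, the unequal period is shorter. The size cannot be known from the documents. Under the assumptions above it is at most about 0.6 of 25 subjects for any TEAE with a 24-hour gap, and much less with a gap of a few hours. Risk concentrated in fewer than 14 days would raise that ceiling. This would not overturn a safety conclusion, but the inequality is written into the collection rule for a stated objective and is easily avoided.

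**What to change.** In Protocol 8.4.1 and 8.4.3 and SAP 4.5.2, for the between-arm comparison:

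- Open AE and SAE collection at randomization in both arms and run it through Day 60.
- Put events before randomization in medical history in both arms.
- Record favipiravir events between randomization and first dose as AEs, flag them as pre-dose and show them separately.
- Define start of treatment for SOC TEAEs as randomization.

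Anchor the SAE window in Protocol 8.4.4 and the partial-date rules in SAP 3.10.2 to randomization for SOC subjects.

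The cost is a short protocol amendment with matching SAP text. A few pre-dose events will appear in the favipiravir column, which the flag makes visible. Protocol 8.4.3 asks for onset dates rather than clock times, so onset time must be captured on Day 1 to place events relative to randomization and first dose.

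Separately, the 14-day follow-up clause in Protocol 8.4.1 and the rule in 8.4.3 that all AEs be followed until resolved, chronic or stable must be reconciled.

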5.4 Individual Stopping Rule

In addition to the above, a. subject should be removed from favipiravir treatment if one of the following criteria is met:

- AST or ALT $> 8 \times ULN$
- ALT or AST > 3 × ULN AND total bilirubin > 2 × ULN
- AST or ALT $> 3 \times ULN$ AND patient has right upper quadrant pain or eosinophilia
- Uric acid > 20mg/dL

A subject whose treatment is terminated should remain in the study for appropriate follow up assessments.

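### Protocol 8.4.1 gives the favipiravir arm alone a 14-day follow-up end point for adverse-event withdrawals, in conflict with 8.4.3; the 8.4.4 SAE window does not fit the SOC arm

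*Protocol*

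**What the plan says.** Five places in the protocol and one in the SAP bear on this.

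- **Protocol 8.4.1, withdrawal for an AE.** Such a subject "shall be followed until the event has resolved or stabilized or, if in the favipiravir arm, 14 days after last dose". The first end point names no arm; the second belongs to favipiravir only.
- **Protocol 8.4.1, recording window.** The investigator "must document all AEs reported through completion of the Day 60 visit", and the treatment-emergent window also runs to Day 60. Neither statement distinguishes the arms.
- **Protocol 8.4.3, general rule.** "The Investigator must follow all AEs until the AE resolves", or until it is judged chronic or clinically stable. For events still open when the study ends, "the Investigator and Medical Monitor will make a clinical assessment to determine whether continued follow-up of the AE is warranted". No arm is named here either.
- **Protocol 5.4, stopping treatment.** "A subject whose treatment is terminated should remain in the study for appropriate follow up assessments".
- **Protocol 8.4.4, SAE reporting.** The window covers "All SAEs as defined below and that occur after the first dose of favipiravir and up to Day 60". No start point is given for SOC subjects.
- **SAP 4.5.2.** Treatment-emergent AEs run to Day 60 and are summarized by subject incidence. The 14-day phrase does not appear.

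**The concern.** Safety against SOC is a secondary objective (Protocol 4.2), and Protocol 9.7 calls for between-arm differences in the proportions of subjects with treatment-emergent, serious and fatal events. Neither Protocol 9.7 nor SAP 4.5.2 describes an adjustment for time under observation, so an event that nobody looked for counts as no event.

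In an open-label trial, a follow-up rule that depends on the assigned arm is a direct route to unequal ascertainment. Subjects who leave because of an AE on favipiravir are also among the most informative about harm. If one site reads the phrase as permission to stop at 14 days and another follows 8.4.3, the outcome, worsening or seriousness of those events is captured unevenly, both between arms and between sites.

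**Working it through.** **1. Reproduce the plan's own window.** Last planned dose on Day 14 plus 46 days of follow-up gives Day 14 + 46 = Day 60. This agrees with 8.4.1 and 8.4.4.

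**2. Locate the 14-day point.** With last dose on Day d, it falls on Day d + 14, which is 60 − (d + 14) days before Day 60.

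| Last dose (d) | d + 14 | Days before Day 60 |
|---|---|---|
| 1 | 15 | 45 |
| 3 | 17 | 43 |
| 8 | 22 | 38 |
| 11 | 25 | 35 |
| 14 | 28 | 32 |

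These 32 to 45 days are a distance to the end of the window. They are not yet a difference between arms.

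**3. Compare the arms under the withdrawal sentence.** Let R be the day on which the event resolves or stabilizes.

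- SOC follow-up ends on Day R. The sentence sets no Day 60 floor for this arm.
- Favipiravir, if the earlier date governs, ends on min(R, d + 14). It is shorter than SOC by max(0, R − (d + 14)).
- Favipiravir, if the later date governs, ends on max(R, d + 14). It is longer than SOC by max(0, (d + 14) − R).

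Take d = 3, so d + 14 = 17, with two values of R assumed purely for illustration:

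| R | SOC ends | Favipiravir, earlier date | Favipiravir, later date |
|---|---|---|---|
| Day 10 | Day 10 | Day 10 (no difference) | Day 17 (7 days longer) |
| Day 30 | Day 30 | Day 17 (13 days shorter) | Day 30 (no difference) |

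On the literal reading, an arm difference appears only if the event is still open at d + 14. On the other reading, it runs the opposite way. Under both, the length of follow-up can depend on the arm.

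**4. Set 8.4.1 beside 8.4.3.** For a favipiravir subject withdrawn with an event open at d + 14, 8.4.3 obliges the investigator to continue, while 8.4.1 read literally permits stopping. No text says which section prevails.

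**5. Scale.** About 50 subjects randomized 1:1 is about 25 per arm, so one subject is 1/25 = 4% of an arm. The documents give no expected number of AE withdrawals or of events open at d + 14, so the total effect cannot be computed.

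**6. SAE start point.** Section 8.4.4 begins at the first favipiravir dose. Sections 8.4.1 and 8.4.3 begin the SOC arm after completion of baseline assessments. Section 8.4.6 requires notification within 24 hours of learning of any SAE, whatever its cause, with no limit by arm. Section 8.4.4 on its own therefore does not fit the SOC arm, but the neighbouring sections largely fill the gap.

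**The case against.** The strongest reply is that the phrase is loose drafting and the rest of the protocol governs. Section 8.4.3 is mandatory and neutral by arm, 8.4.1 itself requires documentation to Day 60, and the SAP does not carry the 14-day phrase forward. The phrase can also be read as a minimum observation period after exposure, which would make favipiravir follow-up equal or longer. Subjects removed from favipiravir under the liver or uric acid criteria stay in the study under 5.4, so an important group for drug harm is untouched. A subject withdrawn for a treatment-emergent AE already counts once for any such event, so longer follow-up of that event leaves that line of the summary unchanged.

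Most of this stands, and it rules out stronger conclusions that a reader might draw:

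- *The favipiravir arm as a whole gets shorter safety follow-up.* The sentence covers only withdrawals from the study for an AE, and its direction is not settled.
- *Favipiravir loses 32 to 45 days relative to SOC.* A withdrawn SOC subject whose event resolves early has no Day 60 floor under the same sentence, so later events can be missed in both arms.
- *Section 5.4 contradicts the 14-day phrase.* It concerns stopping treatment, not leaving the study.
- *SAEs in the SOC arm go unreported.* Sections 8.4.3 and 8.4.6 largely cover them.

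What the reply does not remove is a stated rule that names one arm, conflicts with the general rule two sections later, and leaves sites to choose. The lines for serious events, deaths and outcomes can still change after the withdrawal date, even when the line for any event cannot.

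**Conclusion.** The concern holds in a limited form. For AE withdrawals, 8.4.1 contains an ambiguous end point specific to favipiravir that cannot be reconciled with 8.4.3 as written and sits badly with recording to Day 60. Taken literally, it allows unequal follow-up, confined to events still open 14 days after last dose. The number of subjects is unknown and may be small; early exit is permitted, not required. The SAE start point in 8.4.4 is a separate and smaller drafting gap.

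This conclusion assumes that sites could act on the literal wording. It does not depend on the sample size or on any effect assumption. It is worth correcting because safety ascertainment in an open-label comparison should not depend on arm, and the correction is nearly free.

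**What to change.** 1. In Protocol 8.4.1, delete the arm-specific 14-day phrase so that AE withdrawals in both arms follow the single rule already in 8.4.3.
2. In the same place, state that AE and SAE status will be sought to Day 60 in both arms from withdrawn subjects who still consent to contact, by phone if needed. Protocol 7.6 already allows phone contact at Days 45 and 60. This also closes the gap for withdrawn SOC subjects whose event resolves early.
3. In Protocol 8.4.4, add the SOC start point used in 8.4.1 and 8.4.3, so that the SAE window is defined for both arms.

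The cost is a wording amendment and one or two phone contacts for the few subjects concerned. No visit, procedure or analysis changes, and the Day 60 window in SAP 4.5.2 can stay as it is.
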